4. STUDY DESIGN

4.1. Overall design

[figure not shown]
This study is a Phase III, randomized, open-label, controlled, multicenter US-based study to evaluate the immune response and safety of both HZ/su in healthy adults 50 YOA and older and Flu D-QIV in healthy adults 18 YOA and older when administered sequentially or co-administered with mRNA-1273 booster vaccination.

The study will be conducted in the U.S. and will enroll participants in 2 main study cohorts, HZ/su with mRNA-1273 booster vaccine administered sequentially or concomitantly and Flu D-QIV with mRNA-1273 booster vaccine administered sequentially or concomitantly, hereafter entitled HZ/su and mRNA-1273 booster cohort and Flu D-QIV and mRNA-1273 booster cohort, respectively ([Figure 1](#)).

Potential participants will be triaged initially to either study cohort (HZ/su and mRNA-1273 booster, Flu D-QIV and mRNA-1273 booster) based upon criteria such as seasonal influenza vaccine availability, known eligibility criteria (such as age and vaccination history), and current study enrollment status. Subsequently, enrolled (i.e., having signed an informed consent form) and eligible participants in each cohort will be randomized in a 1:1 ratio to each of the 2 study groups within each cohort ([Table 8](#)). Staggered randomization will be implemented at the beginning of the study for safety monitoring (see Section [8.2.2.1](#)).

- In the HZ/su and mRNA-1273 booster cohort, 546 participants will be randomized in a 1:1 ratio so that 273 participants are assigned to each study group. The first group (**HZ/suSeq group**) will receive the mRNA-1273 booster dose followed approximately 2 weeks later by the first dose of HZ/su, while the second group (**HZ/suCoAd group**) will receive the mRNA-1273 booster dose co-administered with the first dose of HZ/su. All participants in the HZ/suSeq group and the HZ/suCoAd group will receive the second dose of HZ/su approximately 2 months after the first HZ/su dose. Randomization into each group will be stratified by age (50 to 59, 60 to 69, and \geq 70 YOA) and will be set to ensure a minimum number of 138 participants are assigned to the \geq 70 YOA stratum, 69 participants to each group.
- In the Flu D-QIV and mRNA-1273 booster cohort, 1000 participants will be randomized in a 1:1 ratio so that 500 participants are assigned to each study group. The first group (**FluD-QIVSeq group**) will receive the mRNA-1273 booster dose followed approximately 2 weeks later by the Flu D-QIV dose, while the second group (**FluD-QIVCoAd group**) will receive the mRNA-1273 booster dose co-administered with the Flu D-QIV dose. Randomization into each group will be stratified by age (18 to 64 and \geq 65 YOA) and will be set to **target (Amended 21 September 2021)** a minimum number of 150 participants are assigned to the \geq 65 YOA stratum, 75 participants to each group.

All study participants will be followed for safety until 6 months post the last dose of the study vaccine with the total duration of study participation approximately 34 and 26 weeks in the HZ/su and mRNA-1273 booster cohort and Flu D-QIV and mRNA-1273 booster cohort, respectively.

Figure 1 Study design overview

EOS = end of study, telephone contact at 24 weeks post last vaccine dose; N = number of participants enrolled and randomized; PLD = post last dose

*Safety Review Team evaluation of 7 days post-dosing after Visit 1 safety data for initial 10% vaccinated in the HZ/suCoAd group and 5% vaccinated in the FluD-QIVCoAd group prior to full randomization in the respective cohorts
(Amended 21 September 2021)

Table 8 Study groups, intervention, and blinding

Cohort	Study Groups	Number of Randomized Participants	Age	Study Interventions	Blinding
					Visit 1 → Phone Contact 2 (Open-label)*
HZ/su and mRNA1273 Booster	HZ/suSeq	273	≥ 50 years**	mRNA-1273 booster HZ/su	x
	HZ/suCoAd	273			
Flu D-QIV and mRNA-1273 Booster	FluD-QIVSeq	500	≥ 18 years**	mRNA-1273 booster Flu D-QIV	x
	FluD-QIVCoAd	500			

*This is an open-label study; however, the specific participant vaccination schedule (sequential or coadministration) will be randomly assigned within each cohort.

** Randomization will be set to ensure at least 69 participants per group will be ≥ 70 YOA in the HZ/su and mRNA-1273 booster cohort and **to target** at least 75 participants ≥ 65 YOA **per group** in the Flu D-QIV and mRNA-1273 booster cohort. *(Amended 21 September 2021)*

4.2. Scientific rationale for study design

The study was designed after careful considerations of the current healthcare needs and expectations related to vaccinations of the adult population in the U.S.

The U.S Centers for Disease Control and Prevention (CDC) recommends receipt of *Shingrix* to everyone 50 YOA and older, to prevent shingles and its complications [CDC, 2019].

According to CDC, everyone 6 months of age and older should receive a seasonal influenza vaccine every season with rare exceptions. For 2021-2022, CDC recommends use of any licensed, influenza vaccine that is appropriate for the recipient's age and health status, including inactivated influenza vaccine, recombinant influenza vaccine, or live attenuated nasal spray influenza vaccine [[CDC](#), 2021a].

As of summer, 2021, vaccines against COVID-19 in people ages 12 years and older have become an essential part of healthcare procedures to control the COVID-19 pandemic.

With the emergence and spread of the SARS-CoV-2 virus variants that may not be sufficiently controlled by the primary vaccinations, periodic administration of booster COVID-19 vaccines after primary vaccination is either already recommended for specific populations or is under consideration by various health agencies. (Amended 21 September 2021)

Current CDC guidance on the coadministration of COVID-19 vaccines with other routine vaccinations is as follows: "COVID-19 vaccines and other vaccines may now be administered without regard to timing. This includes simultaneous administration of COVID-19 vaccine and other vaccines on the same day, as well as coadministration within 14 days. It is unknown whether reactogenicity of COVID-19 vaccine is increased with coadministration, including with other vaccines known to be more reactogenic, such as adjuvanted vaccines or live vaccines" [[CDC](#), 2021c].

The current study is designed to provide reactogenicity, safety, and immunogenicity data for when a seasonal influenza virus vaccine or an adjuvanted Herpes Zoster subunit vaccine is administered at the same time or two weeks following a potential COVID-19 mRNA booster vaccine. This is important needed data expected to help public health authorities provide more evidence-based guidance and health care providers to make decisions on such vaccine coadministrations.

4.2.1. Rationale for randomization

This will be an open-label study. Comparative analyses between the 2 study groups will only be conducted within each study cohort; therefore, once participants have been triaged to their study cohort, to prevent any selection bias in assignment to each study group, they will be randomly assigned to either the co-administration or sequential study group. Consequently, neither study staff nor participants will be aware which group the participant will be assigned to prior to the randomization.

4.3. Justification for dose

Fluvarix Quadrivalent and *Shingrix* are vaccines licensed by the FDA for use in the U.S and shall be administered in this study as per their approved doses and schedule.

Moderna's mRNA-1273 vaccine is authorized for use in the U.S in adults 18 YOA and older under an EUA by the FDA and as a primary series of two 100 µg doses administered 1 month apart. Doses of 100 µg and 50 µg of the same vaccine are being investigated as a potential booster dose to be administered following the primary series. Preliminary results have shown that a 50 µg mRNA-1273 booster dose at least 6 months following the primary series substantially increases neutralizing antibodies against the wildtype SARS-CoV-2 virus and other tested variants, with a safety profile consistent

with the known profile in earlier clinical trials [Wu, 2021b]. Currently, in light of the evolving emergence of SARS-CoV-2 variants, it is anticipated that a booster vaccine **may be** needed. *The current available data suggests that 50 µg (half dose) of mRNA-1273 may be sufficient to boost immune response against the existing variants. This half dose is now recommended for boosting in the UK for certain populations at high risk for severe disease, to be administered 6 months post the primary series. This dose is also under review by other health agencies.* As a result, 50 µg of mRNA-1273 will be used in this study.

To note: If a different dose of mRNA-1273 is approved and recommended for use as a booster in the US while the study is ongoing, the dose of mRNA-1273 booster in the study will be adjusted in the HZ/su and mRNA-1273 booster cohort to the approved dose. The sample size in this cohort will also be adjusted accordingly to ensure sufficient power to achieve the corresponding primary objectives with the adjusted dose. The data generated with the 50 µg of mRNA-1273 booster will then be informative and add to the body of safety and immunogenicity data at this dose level.
(Amended 21 September 2021)

4.4. End of study definition

A participant is considered to have completed the study if he/she is available for the last scheduled contact as described in the protocol.

The End of Study is defined as the date of the Last Participant Last Visit (LPLV, also may appear as last subject last visit, LSLV) or date of last testing results released of the Human Biological Samples related to primary and secondary endpoints, whichever comes last. End of Study must be achieved no later than 8 months after the LPLV.

5. STUDY POPULATION

Adherence to the inclusion and exclusion criteria specified in the protocol is essential. Deviations from these criteria are not allowed because they can jeopardize the scientific integrity, regulatory acceptability of the study, or safety of the participant.

5.1. Inclusion criteria

All participants must satisfy ALL the following criteria at study entry:

- Participants who in the opinion of the investigator, can and who will comply with the requirements of the protocol (e.g., completion of the eDiaries, return for follow-up visits).
- Written informed consent obtained from the participant prior to performance of any study-specific procedure.
- Age at study entry:
 - **For HZ/su and mRNA-1273 booster cohort:** A male or female aged 50 years or older at the time of randomization.
 - **For Flu D-QIV and mRNA-1273 booster cohort:** A male or female aged 18 years or older at the time of enrollment.

- Healthy participants or medically stable patients as established by medical history and clinical examination at screening. A stable medical condition is defined as disease not requiring significant change in therapy or hospitalization for worsening disease during the 3 months before enrolment.
- Participants who have a documented previous mRNA-1273 primary vaccination series completed (i.e., both doses) at least 6 months prior to first vaccination.
- Female participants of non-childbearing potential (see definition in Section 10.3) may be enrolled in the study. Non-childbearing potential is defined as pre-menarche, current bilateral tubal ligation or occlusion, documented total hysterectomy, bilateral ovariectomy, or bilateral salpingectomy, or post-menopause. Refer to Section 10.3.1 for definitions of women of childbearing potential (WOCBP), menarche and menopause.
- Female participants of childbearing potential may be enrolled in the study, if the participant:
 - Has practiced effective contraception (see definition in Section 10.3) for 1 month prior to study intervention administration, and
 - Has a negative pregnancy test on the day of study intervention administration, and
 - Has agreed to continue effective contraception during the study until 2 months after completion of the study vaccination series.

Refer to Section 10.3.1 for definition of WOCBP and adequate contraception.

5.2. Exclusion criteria

The following criteria should be checked at the time of study entry. The potential participant MAY NOT be included in the study if ANY exclusion criterion applies:

5.2.1. Medical conditions

- Any clinical condition that, in the opinion of the investigator, might pose additional risk to the participant due to participation in the study or might confound post-study intervention administration safety assessments (e.g., tattoos overlying either study intervention administration site).
- History of any reaction or hypersensitivity likely to be exacerbated by any component of the study interventions, including a known history of severe allergic reaction (e.g., anaphylaxis) to any component of any of the study vaccines.
- Any history of Guillain-Barré syndrome.
- Any history of myocarditis or pericarditis.
- Acute or chronic clinically significant pulmonary, cardiovascular, hepatic or renal functional abnormality, as determined by medical history or physical examination.
- Any confirmed or suspected immunosuppressive or immunodeficient condition, based on medical history and physical examination (no laboratory testing required).
- Hypersensitivity to latex.
- For HZ/su and mRNA-1273 booster cohort: history of Herpes Zoster.

5.2.2. Prior/concomitant therapy

- Use of any investigational or non-registered product (drug, vaccine or medical device) other than the study intervention(s) during the period beginning 30 days before the first dose of study intervention(s) (Day -29 to Day 1), or their planned use during the study period.
- Planned administration/administration of a vaccine not foreseen by the study protocol in the period starting 30 days before first dose and ending 30 days after the last dose of study intervention administration. However, **for HZ/su and mRNA-1273 booster cohort:** licensed pneumococcal vaccines and non-replicating vaccines (i.e., inactivated and subunit vaccines, including inactivated and subunit influenza vaccines, with or without adjuvant for seasonal or pandemic flu) may be administered up until 8 days prior to dose 1 of HZ/su and/or dose 2 of HZ/su and/or at least 14 days after any dose of HZ/su. **For Flu D-QIV and mRNA-1273 booster cohort:** licensed pneumococcal vaccines and non-replicating vaccines (i.e., inactivated and subunit vaccines, other than influenza vaccines) may be administered up until 8 days prior to dose 1 of Flu D-QIV and/or at least 30 days after any dose of Flu D-QIV. For time interval between other routine vaccines with mRNA-1273 booster dose (administered in the study), local guidelines must be followed.

In case emergency mass vaccination for an unforeseen public health threat (e.g., a pandemic) is organized by public health authorities outside the routine immunization program, the time period described above can be reduced if necessary for that mass vaccination vaccine, provided this vaccine is licensed and used according to its Product Information.

- Administration of long-acting immune-modifying drugs at any time during the study period (e.g., infliximab).
- Administration of immunoglobulins and/or any blood products or plasma derivatives during the period starting 3 months before the first dose of study intervention(s) up to 1 month post-last dose or planned administration during the study period.
- Prior planned or chronic administration (defined as more than 14 days in total) of immunosuppressants or other immune-modifying drugs during the period starting 3 months prior to the first vaccine. For corticosteroids, this will mean more than 14 days in total of prednisone ≥ 20 mg/day or equivalent is not allowed. Inhaled, intra-articular and topical steroids are allowed.
- **For HZ/su and mRNA-1273 booster cohort:** Previous vaccination against Herpes Zoster with the exception of receipt of live attenuated HZ vaccine.
- **For Flu D-QIV and mRNA-1273 booster cohort:** Administration of a seasonal influenza vaccine during the 6 months preceding entry into the study.
- Prior administration of an investigational or licensed coronavirus (SARS-CoV, MERS-CoV, SARS-CoV-2) vaccine **except for mRNA-1273 vaccine.**
- Any contraindication to the study intervention(s).

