HZ/su and mRNA-1273 PPS - (For Hz/su and mRNA-1273 booster cohort)	
The HZ/su and mRNA-1273 PPS will include all participants from the HZ/su and mRNA-1273 Exposed Set
 
▪ Who meet all eligibility criteria;▪ Who receive all doses of study interventions according to their random assignment;▪ For whom administration site of study vaccine is known;▪ Who do not receive any other prohibited concomitant medication/vaccine up to blood sample post HZ/su dose 2;▪ Who comply with the procedures and intervals defined in the protocol and allowed for analysis up to blood sample post HZ/su dose 2;▪ Who do not meet any of the criteria for elimination up to blood sample post HZ/su dose 2;▪ For whom data concerning immunogenicity endpoint measures are available at post vaccination for either mRNA-1273 booster or HZ/su dose 2. 
Note: Subjects qualify for HZ/su PPS and mRNA-1273 PPS independently, meaning, if the criterion to exclude a participant from the HZ/su and mRNA-1273 PPS only applies to one analysis e.g., HZ/su and not mRNA-1273 by virtue of a participant missing the HZ/su primary endpoint blood draw four weeks after the second dose, then the participant will be excluded only from the applicable PPS subset, i.e., in this example, excluded only from the HZ/su PPS subset and maintained in the mRNA-1273 PPS subset..

Flu D-QIV and mRNA-1273 Exposed Set (For Flu D-QIV and mRNA-1273 booster cohort)	The Flu D-QIV and mRNA-1273 Exposed Set will include all participants in the Flu D-QIV and mRNA-1273 booster cohort with at least 1 vaccine administration documented. The Exposed Set analysis will be performed per vaccine(s) actually administered (at Day 1).

	
The Flu D-QIV and mRNA-1273 Exposed Set for analysis of immunogenicity will include vaccinated participants for whom immunogenicity data are available.

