9.1.1. Solicited Adverse Events

Solicited AEs are pre-specified local and systemic adverse events. Solicited AEs will be collected through 7 days following each vaccination. Solicited AEs with onset during the 7-day solicitation period that continue beyond the 7-day period will be reported as solicited AEs. The solicited AEs will be collected using the diary eCRFs.

Participant's compliance with respect to the diary card based on the Exposed Set will be determined separately for local and systemic events for the following:

- Number of participants who did not present diary data at all
- Number of participants who completed diary card, regardless of visit
- Number of participants who completed diary card for each day of the first 7 days post any vaccination (i.e., Day 1, Day 2, Day 3, Day 4, Day 5, Day 6 and Day 7)

A sensitivity analysis to exclude participants who may not have acceptable diary data or certain missing diary records may be performed.

Per the study design and diary forms, participants who receive the administration of the mRNA-1273 booster vaccine on Day 1, have until Day 14 (Week 2) to receive the next vaccine administration. As such, all solicited systemic AEs that occurred on or after mRNA-1273 booster vaccine but prior to HZ/su or Flu D-QIV vaccine administration on Day 14 (Week 2) are deemed to be attributable to the mRNA-1273 booster vaccine. For participants in the sequential groups (HZ/suSeq, FluD-QIVSeq), the diary forms are re-set at the time of first HZ/su or Flu D-QIV vaccination on Day 14 (Week 2) to collect solicited systemic AEs that are either ongoing from mRNA-1273 booster vaccine from Day 1 or occurred on or after the first HZ/su or Flu D-QIV vaccination on Day 14 (Week 2). The diary data is therefore setup to ensure that any solicited systemic AE attributable to each of the following vaccines only: mRNA-1273 booster, first HZ/su, second HZ/su or Flu D-QIV, can be determined depending on the time of the AE relative to the time of each vaccine administration, and prior to the date of any subsequent vaccination. Solicited local AEs are collected in separate diaries per vaccine received and will be attributed to the appropriate based on the diary used.

For data analysis purposes, the CoAd groups (HZ/suCoAd, FluD-QIVCoAd) will be presented as a single column, with the exception of the HZ/suCoAd group that certain selected outputs will be displayed by the first and second HZ/su vaccine doses respectively.

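### The exception for non-study vaccines is counted from HZ/su or Flu D-QIV rather than from the first study vaccination, so around the booster it works differently in the two arms

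*Protocol*

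**What the plan says.** Protocol Section 5.2.2 first sets a default: vaccines outside the protocol are barred "in the period starting 30 days before first dose and ending 30 days after the last dose of study intervention administration". The first dose is the booster on Day 1 in every group, so the start of this ban does not depend on the arm.

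The exception is counted differently. In the HZ/su cohort, licensed pneumococcal and non-replicating vaccines (influenza vaccines included, adjuvanted or not) "may be administered up until 8 days prior to dose 1 of HZ/su and/or dose 2 of HZ/su and/or at least 14 days" following an HZ/su dose. In the Flu D-QIV cohort the same types, with influenza vaccines excepted, "may be administered up until 8 days prior to dose 1 of Flu D-QIV and/or at least 30 days after any dose of Flu D-QIV". Spacing from the booster has no protocol interval: "For time interval between other routine vaccines with mRNA-1273 booster dose (administered in the study), local guidelines must be followed". The national guidance cited in Protocol Section 4.2 reads "COVID-19 vaccines and other vaccines may now be administered without regard to timing".

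Protocol Table 2 places the first HZ/su or Flu D-QIV dose on Day 1 in CoAd and at Week 2 in Seq. Section 5.2 has the exclusion criteria checked at study entry. Section 4.2.1 says that nobody knows the arm before randomisation, which Table 1 puts at Visit 1.

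The per-protocol sets (PPS) in SAP Section 4.3 require all eligibility criteria to be met. In the HZ/su cohort they keep participants "Who do not receive any other prohibited concomitant medication/vaccine up to blood sample post HZ/su dose 2", with a similar line for Flu. SAP Section 9.1.1 says that systemic solicited events in the Seq groups that occur after the booster but "prior to HZ/su or Flu D-QIV vaccine administration on Day 14 (Week 2) are deemed to be attributable to the mRNA-1273 booster vaccine".

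**The concern.** The default ban and its exception use different starting points, and only the exception's starting point moves with the arm. Three things follow.

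- **Eligibility.** A site must judge a recent or planned exempt vaccination before it knows which date the limit is counted from.
- **Control condition.** Hypotheses 2 and 4 compare the booster given with another vaccine against the booster given alone. The rule allows a Seq control another vaccine on the booster day: an influenza vaccine in HZ/suSeq, or another non-replicating vaccine in FluD-QIVSeq. Because that vaccine is permitted, the control stays in the mRNA-1273 PPS. A CoAd participant vaccinated on the same date breaches the criterion and can leave the PPS.
- **Reactogenicity.** Systemic reactions to the extra vaccine would be counted in the Seq mRNA-1273 column.

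At stake is whether the anti-S comparison contrasts the conditions it names, and whether PPS membership is decided by the same rule in both arms.

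**Working it through.** **Inputs.** Anti-S SD 0.45 (log10), assumed ratio 1.1, margin 1.5, one-sided alpha 0.025, and 245 (HZ/su) or 450 (Flu) evaluable per group: Protocol Tables 18 and 19. Visit 1 to Visit 2 planned at 14 days, allowed 14–21: Protocol Tables 4 and 5. Section 5.2.2 equates 30 days before the first dose with Day -29, so Day 0 exists and 8 days before Day 1 is Day -7.

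**Step 1: reproduce the plan's power for anti-S.** SE = 0.45 × √(2/n).

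- HZ/su: SE = 0.0407; (0.1761 − 0.0414)/0.0407 = 3.313. The t-based power is 91.1%, as stated (normal approximation 91.2%).
- Flu: SE = 0.0300; 0.1347/0.0300 = 4.490. Power is 99.4%, as stated.

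The inputs are therefore read correctly.

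**Step 2: day count at the planned visits.** Last permitted day = anchor day − 8. First permitted day afterwards = anchor day + 14 (HZ/su) or + 30 (Flu D-QIV).

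| Group | Anchor dose | Last permitted before | First permitted after |
|---|---|---|---|
| HZ/suCoAd | Day 1 | Day -7 | Day 15 |
| HZ/suSeq | Day 15 | Day 7 | Day 29 |
| FluD-QIVCoAd | Day 1 | Day -7 | Day 31 |
| FluD-QIVSeq | Day 15 | Day 7 | Day 45 |

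- Permission differs by arm from Day -6 to Day 7, which is 14 days and includes the booster day. If Visit 2 falls at 21 days (Day 22), the Seq limit moves to Day 14.
- Example: an exempt vaccine on Day -3 is 4 days before HZ/su in CoAd (barred) and 18 days before it in Seq (allowed).
- The HZ/su cohort also has a reverse asymmetry. The Week 4 anti-S sample is planned for Day 29. HZ/suCoAd may receive an exempt vaccine from Day 15, before that sample, and HZ/suSeq not until Day 29. In the Flu cohort the CoAd allowance restarts on Day 31, after the planned sample.
- Counted from Day 1 in both arms, the arm-dependent interval would be 0 days.

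**Step 3: illustration of size.** The documents give neither uptake nor interference, so both are assumed. Let a share f of Seq controls receive a vaccine with the booster that lowers anti-S as much as the study vaccine does, let CoAd have no such uptake, and let the true Seq/CoAd ratio be 1.5. The expected observed ratio is 1.5^(1−f), and the chance of declaring non-inferiority is Φ(f × 0.1761/SE − 1.96).

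| f | HZ/su, n = 245 | Flu, n = 450 |
|---|---|---|
| 0% | 2.5% | 2.5% |
| 2% | Φ(−1.873) = 3.1% | Φ(−1.843) = 3.3% |
| 5% | Φ(−1.743) = 4.1% | Φ(−1.667) = 4.8% |
| 10% | Φ(−1.527) = 6.3% | Φ(−1.373) = 8.5% |
| 20% | Φ(−1.094) = 13.7% | Φ(−0.786) = 21.6% |

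If the extra vaccine multiplies anti-S by 0.8 instead, f = 10% and 20% give 4.3% and 6.9% (HZ/su), and 5.1% and 9.4% (Flu). With no uptake or no interference the effect is nil.

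**The case against.** The strongest reply accepts the text but disputes the consequences. Much of it stands.

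- **Direction.** A reader might infer that the rule pulls the ratio towards 1 and favours non-inferiority. That holds only if the extra vaccine lowers anti-S and uptake falls in Seq. In the HZ/su cohort the CoAd allowance from Day 15 can work the other way, so the documents do not settle the sign.
- **Duration.** A reader might also infer from the 49- and 42-day limits in SAP Tables 8 and 9 that the Seq allowance can cover the whole interval to Week 4. Those are tolerances for staying in the PPS. Within the protocol's 14–21 day window the allowance ends on Day 7 to Day 14.
- **Safety.** Only systemic solicited events are affected. SAP Section 9.1.1 collects local events in a separate diary per vaccine, and all safety analyses are descriptive.
- **Existing provisions.** SAP Amendment 1, Section 8, repeats all immunogenicity summaries on the Exposed Set, so differential PPS exclusion would show there. Protocol Section 9.3.8.1 plans percentages using concomitant medication or vaccination within 7 and 30 days of each administration. The Exposed Set does not undo an extra vaccine in the control arm, and those percentages do not isolate vaccines given around the booster.
- **Workaround.** A site could apply the CoAd limit to everyone before randomisation, and stricter local guidance would narrow the gap. The protocol asks for neither, and recent vaccination is not among the reasons for delay in Section 5.5.

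The reply does not remove the arm-dependence itself.

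**Conclusion.** The point holds as a defect in the rule. The exception in Section 5.2.2 permits or bars the same vaccination, on the same date, according to an arm not yet assigned. At the planned visits this covers Day -6 to Day 7 in both cohorts. It lets a control meant to receive the booster alone have another vaccine with it and remain in the mRNA-1273 PPS. It concerns exempt vaccines only; other vaccine types stay under the Day 1 default.

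The documents do not show that Hypotheses 2 and 4 are biased, or in which direction. The error rates above rest on assumed uptake in Seq only, assumed interference and a true ratio exactly at the margin. They show what the rule would allow and do not forecast what will happen. The issue deserves correction because the arm-dependence is certain and the correction is cheap.

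**What to change.** **Protocol Section 5.2.2.** Reconcile the exception with the Day 1 default and with randomisation at Visit 1. One calendar window, anchored to the first study vaccination, should apply to both arms of a cohort through the Week 4 anti-S sample and be checkable before randomisation. Its length is for the sponsor to set.

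**SAP.**

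- Tabulate non-study vaccine receipt around the booster by arm, extending the percentages planned in Protocol Section 9.3.8.1. SAP Section 7.1 currently plans only listings.
- Add a sensitivity analysis of Hypotheses 2 and 4 that applies the same non-study-vaccine window to both arms, beside the PPS and Exposed Set analyses. This is preferable to a new PPS elimination rule: for participants enrolled under arm-dependent permissions, such a rule would be another post-randomisation exclusion that could fall unequally.
- Flag such receipt for the Seq mRNA-1273 column of solicited systemic events.

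**Cost.** A short amendment to Section 5.2.2, one table, one sensitivity analysis and one flag. Protocol Section 6.8 already has vaccinations recorded with dates, so no new data are needed. The sensitivity analysis will have slightly fewer participants, and some Seq participants who want another vaccine will wait a short time.
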